6.4 Concomitant Medications

Concomitant medications will be reviewed with the subject at Baseline (Day 0; within 24 hrs of transplant), 30 days post-transplant, and 6 months post-transplant. Eligibility to participate in the study will not be prohibited based on medication alone. Concomitant medications will also be captured for the 2-week period prior to the onset of a serious adverse event (SAE).

6.5 Physical Examination

Physical examination(s) should be performed by the Study Center for all patients as a standard of practice prior to listing patient for transplantation.

A physical examination should be performed at the Baseline Visit. Symptom-directed physical examinations will be performed again at Day 30 and Month 6 post-transplant. Any values judged by the Investigator to be clinically significant abnormal changes from Baseline (before study intervention) should also be recorded on the Adverse Event CRF as an AE.

Specific tests to assess lung capacity will also be obtained and recorded on the CRF. Upon admission to the ICU, the subject's initial PaO₂ is to be recorded.

FEV₁, measured as a percentage of predicted normal value, and oxygen required at rest are to be recorded at the time of hospital discharge (if prior to 30 days post-transplant), Day 30, Day 90, Month 6, and Year 1 post-transplant, and premature discontinuation (if applicable).

In addition, after completion of the Analysis Phase, FEV₁ and oxygen at rest will be collected annually by the Sponsor for the Long-term Follow-up Phase (Year 2, 3, 4, and 5).

6.6 Vital Signs

Assessments of vital signs are to be collected at each scheduled study visit. The following vital sign parameters should be recorded: height (baseline only), weight, heart rate, blood pressure, respiration rate, and oxygen saturation.

Heart rate, blood pressure, respiration rate, and oxygen saturation will be measured after the subject has been seated at rest for at least 5 minutes. Systemic blood pressures may be obtained by cuff, and systemic arterial oxygen saturation may be obtained by pulse oximetry.

6.7 Primary Graft Dysfunction Score

The subject's PGD Score is to be determined by the Investigator at Baseline (Day 0) after transplantation and upon admission to the ICU, as well as 24, 48, and 72 hrs post-transplant. [Christie 2005]

PGD Score will be as graded using the parameters in Table 2, where the P/F ratio is PaO₂/FiO₂.

Table 2. Primary Graft Dysfunction Grading

Grade	P/F Ratio	Chest X-ray
0	>300	Normal
1	>300	Diffuse allograft infiltrates
2	200-300	Diffuse allograft infiltrates
3	<200	Diffuse allograft infiltrates

If the subject is on ECMO at any time point, the PGD grade is automatically assessed as “3”.

If the subject has been extubated prior to assessment, the presence or absence of radiographic infiltrates consistent with pulmonary edema will be reviewed and graded as follows for the PGD Grade:

- If subject is extubated AND the chest x-ray is “Absent” of infiltrates, then the PGD Score is 0.
- If subject is extubated AND the chest x-ray is “Present” of infiltrates, then the PGD Score is 1.

Graft survival will be evaluated by the Investigator (or his/her designee) at Day 30, Day 90, Month 6, Year 1 post-transplant, and premature termination (if applicable). Graft survival will be measured as functioning or failed. If the graft fails within first year post-transplant, the date of graft failure will be collected. The primary cause of graft failure will also be captured as one of the following:

- Primary Non-Function
- Acute Rejection
- Chronic Rejection
- or Other: (if Other, Specify)

After completion of the Analysis Phase, Graft Survival will be evaluated and collected annually by the Sponsor for the Long-term Follow-up Phase (Year 2, 3, 4, and 5).

6.8 Survival

Subject survival, measured as living or dead, will be recorded Day 30, Day 90, Month 6, and Year 1 post-transplant. If the subject expires within first year post-transplant, the date of death and primary cause of death will be collected.

After completion of the Analysis Phase, subject survival will be collected annually by the Sponsor for the Long-term Follow-up Phase (Year 2, 3, 4, and 5).

6.9 Bronchiolitis Obliterans Syndrome Grade

During the Analysis Phase, evaluation of BOS will be conducted by the Investigator (or his/her designee) at Day 90, Month 6, Year 1 post-transplant, and premature termination (if applicable). Assessment will be noted as one of the following:

- NO BOS
- Yes, Grade 0-p
- Yes, Grade 1
- Yes, Grade 2
- Yes, Grade 3
- Yes Grade Unknown (UNK)
- Unknown

After completion of the Analysis Phase, BOS Grade will be collected annually by the Sponsor for the Long-term Follow-up Phase (Year 2, 3, 4, and 5).

6.10 Physical Capacity

During the Analysis Phase, evaluation of physical capacity will be conducted by the Investigator (or his/her designee) at Day 90, Month 6, Year 1 post-transplant, and premature termination (if applicable). Assessment will be noted as one of the following:

- No Limitations
- Limited Mobility
- Wheelchair bound or more limited
- Hospitalized
- UNK

After completion of the Analysis Phase, Physical Capacity will be collected annually by the Sponsor for the Long-term Follow-up Phase (Year 2, 3, 4, and 5).

6.11 Work Status

During the Analysis Phase, evaluation of work status will be conducted by the Investigator (or his/her designee) at Day 90, Month 6, Year 1 post-transplant, and premature termination (if applicable). Assessment will be noted as one of the following:

- Working Full-time
- Working Part-time due to Demands of Treatment
- Working Part-time due to Disability
- Working Part-time due to Insurance Conflict
- Working Part-time due to Inability to Find Full-time Work
- Working Part-time due to Subject Choice
- Working Part-time Reason UNK
- Working Part-time vs. Full-time UNK

After completion of the Analysis Phase, Work Status will be collected annually by the Sponsor for the Long-term Follow-up Phase (Year 2, 3, 4, and 5).

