2.3 Other Objective(s)

Additional objectives of this study include evaluation of intermediate and longer-term safety and preliminary efficacy in subjects receiving a lung transplant where the lung(s) was perfused using the TES performed by the Sponsor. Assessments will include the following:

- Initial ICU partial pressure of oxygen in arterial blood (PaO₂): Evaluated as first PaO₂ measured after ICU admission.
- Forced Expiratory Volume in one second (FEV₁) evaluated at time of discharge, 30 days, 90 days, 6 months and 1 year post-transplant. FEV₁ is measured as a percentage of predicted normal value.
- Oxygen requirement at rest evaluated at time of discharge, 30 days, 90 days, 6 months and 1 year post-transplant. Oxygen required at rest is measured in liters per minute (L/min).
- Subject survival evaluated at 90 days, 6 months, and 1 year post-transplant. Measured as living or dead. If the subject expires within first year post-transplant, the date of death and primary cause of death will be collected.
- Graft survival evaluated at 30 days, 90 days, 6 months, and 1 year post-transplant. Measured as functioning or failed. If the graft fails within first year post-transplant, the date of graft failure will be collected.
- Primary cause of graft failure evaluated at 30 days, 90 days, 6 months, and 1 year post-transplant on all failed grafts.
- Bronchiolitis Obliterans Syndrome (BOS) Grade evaluated at 90 days, 6 months, and 1 year post-transplant.
- Number of re-hospitalizations after transplant evaluated at 6 months and 1 year post-transplant. Measured as total number of hospitalizations since initial discharge.
- Physical capacity evaluated at 90 days, 6 months, and 1 year post-transplant.
- Working for income after transplant evaluated at 90 days, 6 months, and 1 year post-transplant.

The above information will also be collected on patients enrolled in a contemporaneous control group to provide context for EVLP results and to inform control measures for future research.

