7.3.5 Visit 5 Procedures (Day 90 post-transplant)

On Day 90 post-transplant (\pm 10 days), the Investigator or his/her designee should record the following:

- Subject and graft survival and if failed, cause of failure
- FEV₁
- Oxygen required at rest
- BOS Grade
- Physical capacity

- Working for income status
- Hospital readmission date(s) (if applicable)
- Assess AEs

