9.7 Exploratory Endpoints

Other safety endpoints that will be analyzed include:

- Initial ICU PaO₂: Evaluated as first PaO₂ measured after ICU admission.
- FEV₁: Evaluated at time of discharge, 30 days, 90 days, 6 months and 1 year post-transplant. FEV₁ is measured as a percentage of predicted normal value.

- Oxygen Requirement at Rest: Evaluated at time of discharge, 30 days, 90 days, 6 months and 1 year post-transplant.
- Subject Survival: Evaluated at 90 days, 6 months and 1 year post-transplant. Measured as living or dead. If the subject expires within first year post-transplant, the date of death and primary cause of death will be collected.
- Graft Survival: Evaluated at 30 days, 90 days, 6 months and 1 year post-transplant. Measured as functioning or failed. If the graft fails within first year post-transplant, the date of graft failure will be collected.
- Primary Cause of Graft Failure: Evaluated at 30 days, 90 days, 6 months and 1 year post-transplant on all failed grafts.
- Bronchiolitis Obliterans Syndrome (BOS) Grade: Evaluated at 90 days 6 months and 1 year post-transplant.
- Number of Re-hospitalizations after Transplant: Evaluated at 6 months and 1 year post-transplant. Measured as total number of hospitalizations since initial discharge.
- Physical Capacity: Evaluated at 90 days, 6 months and 1 year post-transplant.
- Working for Income after Transplant: Evaluated at 90 days, 6 months and 1 year post-transplant.

All exploratory endpoints will be presented using descriptive statistics along with two sided 95% CIs by Transplant Group. Other supportive endpoints may be included as needed.

Results may be displayed graphically. There will be no inferential testing conducted.

In addition, supplemental analyses comparing the EVLP group and the Control Group may be performed to provide context of results observed in this study (details will be described in the SAP).

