6.3 Exploratory Endpoints and Analyses

Other safety endpoints that will be analyzed include:

- Initial ICU PaO₂: Evaluated as first PaO₂ measured after ICU admission.
- FEV₁: Evaluated at time of discharge, 30 days, 90 days, 6 months and 1 year post-transplant. FEV₁ is measured as a percentage of predicted normal value. Oxygen Requirement at Rest: Evaluated at time of discharge, 30 days, 90 days, 6 months and 1 year post-transplant.
- Subject Survival: Evaluated at 90 days, 6 months and 1 year post-transplant. Measured as living or dead. If the subject expires within first year post-transplant, the date of death and primary cause of death will be collected.
- Graft Survival: Evaluated at 30 days, 90 days, 6 months and 1 year post-transplant. Measured as functioning or failed. If the graft fails within first year post-transplant, the date of graft failure will be collected.
- Primary Cause of Graft Failure: Evaluated at 30 days, 90 days, 6 months and 1 year posttransplant on all failed grafts.
- Bronchiolitis Obliterans Syndrome (BOS) Grade: Evaluated at 90 days 6 months and 1 year post-transplant.
- Number of Re-hospitalizations after Transplant: Evaluated at 6 months and 1 year post-transplant. Measured as total number of hospitalizations since initial discharge, the number of re-hospitalizations per subject, and whether the subject had a re-hospitalization related to transplant.
- Physical Capacity: Evaluated at 90 days, 6 months and 1 year post-transplant.
- Working for Income after Transplant: Evaluated at 90 days, 6 months and 1 year post-transplant.

Initial ICU PaO₂ and FEV₁ will be presented using descriptive statistics by Transplant Group. All other exploratory endpoints are categorical and will be summarized by presenting the number of subjects and percentage for each category. Other supportive endpoints may be included as needed.

Results may be displayed graphically. There will be no inferential testing conducted.

In addition, supplemental analyses comparing the EVLP group and the Control Group may be performed to provide context of results observed in this study.

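### The work-status list in Protocol 6.11 has no option for a recipient who is not working, so the exploratory endpoint of working for income cannot be read as planned

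*Protocol*

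**What the plan says.** Working for income is a named endpoint. Protocol 2.3 lists it among the other objectives ("Working for income after transplant evaluated at 90 days, 6 months, and 1 year post-transplant"), Protocol 9.7 lists it as exploratory ("Working for Income after Transplant: Evaluated at 90 days, 6 months and 1 year post-transplant"), and SAP 6.3 carries it over ("Working for Income after Transplant: Evaluated at 90 days", with the same two later visits). The Day 90, Month 6 and Year 1 visit sections of the protocol ask the site to record "Working for income status" but give no response set.

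The only response set in either document is in Protocol 6.11. The rule is "Assessment will be noted as one of the following", followed by eight options. The first is "Working Full-time", the next six are part-time work with a stated or unknown reason, and the last is "Working Part-time vs. Full-time UNK".

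For analysis, SAP 6.3 says: "All other exploratory endpoints are categorical and will be summarized by presenting the number of subjects and percentage for each category". SAP 4.2 runs all analyses on the full analysis set, meaning all enrolled subjects. SAP 4.4 leaves missing data missing outside the primary graft dysfunction endpoint. No denominator is stated for this percentage.

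**The concern.** An endpoint about whether recipients work for income has to be able to record that a recipient does not. Under 6.11 as written it cannot. Even the options marked unknown assert that the subject works; only the reason or the hours are unknown.

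The protocol itself expects recipients who are unlikely to be working. The physical capacity list in 6.10, used at the same visits, includes being hospitalised and being confined to a wheelchair. Protocol 4.2 sets a minimum age of 18 and no maximum, so retired recipients are eligible. For such a person the site must choose a wrong category or leave the item blank, and the plan does not say which.

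At stake is whether the return-to-work table can be read in either group. Protocol 2.3 says the control data are also meant to inform control measures in future research, and a rate with no valid negative answer serves that purpose poorly.

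**Working it through.** The documents give no rate, power or sample size for this endpoint, so there is no plan figure to reproduce. The check has two parts.

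**1. Count the options.** Options in Protocol 6.11: 8. Options that state the subject is working: 8. Options for not working: 0. Options for an overall unknown: 0. By comparison, the bronchiolitis obliterans syndrome list in 6.9 has both a negative and an unknown option, and the physical capacity list in 6.10 has an unknown option.

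**2. Follow a non-worker into the table.** Inputs:
- Group size: 66 (Protocol 9.2, SAP 9).
- True share working among those assessed: not in the documents; assumed 10% to 50%.
- Number assessed at a visit: not in the documents; assumed 66 (all) or 59 (about 90%).
- Number working = number assessed × share working, rounded. With 66 assessed this is 7 to 33; with 59 assessed it is 6 to 30.

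| How a non-worker is recorded | Denominator | Reported % working, 66 assessed | Reported % working, 59 assessed |
|---|---|---|---|
| Forced into a listed option | Those assessed | 66/66 = 100% | 59/59 = 100% |
| Forced into a listed option | All enrolled | 66/66 = 100% | 59/66 = 89.4% |
| Left blank | Recorded answers | 7/7 to 33/33 = 100% | 6/6 to 30/30 = 100% |
| Left blank | All enrolled | 7/66 to 33/66 = 10.6% to 50.0% | 6/66 to 30/66 = 9.1% to 45.5% |

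The first three rows do not respond to the true share at all. The fourth does, but its blanks are a mixture. For example, with 59 assessed and an assumed 30% working, 18 are recorded as working and 66 − 18 = 48 are blank. Of these, 59 − 18 = 41 are non-workers and 66 − 59 = 7 died or were not assessed. The table shows only the 48.

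With a not-working option added, the percentage among those assessed recovers the assumed share: 7/66 = 10.6% for 10%, 13/66 = 19.7% for 20%, 20/66 = 30.3% for 30%, and 33/66 = 50.0% for 50%.

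**The case against.** A reader might infer that the endpoint will come out at about 100% and carry no information. The documents do not establish that. It needs either a forced choice among the listed options or a denominator of recorded answers, and neither is stated. SAP 4.2 points towards all enrolled subjects. SAP 4 mentions the number of non-missing observations only for continuous variables. Leaving missing data missing means no imputation; it does not by itself remove anyone from the denominator. If non-workers are left blank, the counts of full-time and part-time workers survive, and with 66 per group they give the smallest share that can be working. This part of the objection stands: the 100% result is conditional.

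Secondly, the case report form is not among the documents. The visit item is worded so that it could be a yes/no question, with the 6.11 list as detail for those who answer yes. That is possible and should be checked, but neither document says so, and 6.11 is the only specification given. For Years 2 to 5 the data come from national registry follow-up forms (Protocol 10.11.2.3), so the 6.11 list need not govern those years.

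Thirdly, this is one of ten exploratory items and is descriptive only. The halting rules and the data submitted for the early regulatory safety review do not use it either. That limits the severity but does not remove the gap.

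**Conclusion.** The gap in the list is real and can be checked on the page without any assumption: as specified, not working cannot be recorded. The consequence depends on two things the plan leaves open, namely how sites handle a non-worker and which denominator is used. The reported percentage is then either about 100% by construction (89.4% of all enrolled if 59 of 66 are assessed and a listed option is forced) or a figure that tracks the true share while merging non-workers with deaths and missing forms. The assumed shares of 10% to 50% and the 59 assessed are illustrations, not figures from the documents.

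The conclusion also rests on the case report form having no separate yes/no item, which cannot be verified here. Severity is minor.

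**What to change.** - **Protocol 6.11 and the case report form:** add an option for not working and one for unknown. If the form already holds a yes/no/unknown item on working for income, no new option is needed; name that item in 6.11 as the endpoint variable and describe the existing list as detail for those who answer yes.
- **SAP 6.3:** list the categories to be tabulated as working, not working, and unknown or missing, with deaths shown separately, and state the denominator. All enrolled subjects or those alive at the visit are both defensible, provided the choice is stated.
- **Visits already recorded:** SAP 8 shows that a 90-day safety report went to the regulator in July 2017, and SAP version 2.0 was signed in January 2020, so a change to the list will not repair past entries. Either recover non-working status from source documents, or state with the table that a blank cannot be read as not working.

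The cost is a correction to the list and a few lines in the SAP, with no extra visit or procedure. Going back to source is the only real effort, and it is optional if the limitation is stated.

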6.12 Clinical Laboratory Tests

6.12.1 Laboratory Parameters

During the EVLP lung evaluation, perfusate blood gas will be collected by the EVLP Specialist hourly to assess PCO₂, PO₂ and pH both distally and proximally to the lung to assess the lung's capacity to effectively exchange gas (see [Appendix 4](#), ABG Analyzer). The Sponsor's facility will test perfusate blood gas samples using a Siemens RapidPoint 500 ABG analyzer.

Subject (recipient post-transplant) arterial blood gases (ABGs) must be determined by the Investigator, in order to calculate PGD grade (Section 6.7), at Baseline (Day 0, within 24 hrs of transplant), and 24, 48, and 72 hrs post-transplant. Laboratory results for tests performed as part of PGD scoring for this study and will be recorded on the Primary Graft Dysfunction CRF with the date and the time the assessment was performed.

6.12.2 Sample Collection, Storage, and Shipping

The Sponsor will collect pre- and post-EVLP donor lung biopsies for future analysis or quality assurance (QA), and/or if requested/ required by transplanting center. Additionally, perfusate samples will be collected from the EVLP perfusion circuit for QA and future analysis. Samples will be identified by donor ID number. Consent for collecting and storing donor lung samples pre-transplantation for future research purposes will be obtained from the donor's Legal Next of Kin (Section 10.4.1).

6.13 Safety Reporting

This study is designed to evaluate the safety of extending the preservation and assessment time of donor lungs using the TES as administered by the Sponsor in a dedicated and centralized facility. Subjects enrolled in this study suffer from end-stage lung failure where the only available treatment is lung transplantation.

6.13.1 Definitions

Adverse Events

An adverse event (AE) is any untoward medical occurrence, unintended disease or injury, or any untoward clinical signs (including abnormal laboratory findings) in a clinical investigation subject which does not necessarily have a causal relationship to the investigational medical device. All AEs are assessed by the Study Centers for severity, causality, outcome, seriousness, and if unanticipated, documented as such (see below).

Serious Adverse Event (SAE)

A serious adverse event (SAE) is defined by federal regulation as any AE that results in any of the following outcomes: death, life-threatening AE, hospitalization or prolongation of existing hospitalization, a persistent or significant disability/incapacity, or a congenital anomaly/birth defect.

Important medical events that may not result in death, be life threatening, or require hospitalization may be considered an SAE when, based upon appropriate medical judgment, they may jeopardize the subject and may require medical or surgical intervention to prevent one of the outcomes listed in this definition. Examples of such medical events include allergic bronchospasm requiring intensive treatment in an emergency room or at home, blood dyscrasias or convulsions that do not result in inpatient hospitalization, or the development of drug dependency or drug abuse.

Unanticipated Adverse Device Effect (UADE)

Any serious adverse device effect on health or safety or any life-threatening problem or death caused by or associated with a device, if that effect, problem, or death was not previously identified in nature, severity, or degree of incidence in the investigational plan or application (including a supplementary plan or application), or any other unanticipated serious problem associated with a device that relates to the rights, safety, or welfare of subjects.

Anticipated Adverse Events not Related to EVLP

Anticipated Adverse Events not related to EVLP are events inherent to the lung transplant surgical procedure and immunosuppressant medications that are expected to occur throughout the initial post-hospital stay in all subjects.[Lyu 2009] These events do not require reporting and are not considered AEs as defined or described elsewhere in this protocol. For the purposes of this protocol, Anticipated Adverse Events not related to EVLP are:

- Surgical
 - Anesthesia related nausea/vomiting
 - Surgical incision, thoracotomy, incision-related pain and bleeding
 - Moderate bruising at surgical site
 - Chest tube placement, chest tube pain
 - Surgical lines, including arterial, Swan-Ganz catheter, triple lumen catheter
 - Ventilator use during and after surgery
 - Back pain related to operating room table or referred pain
- Gastrointestinal
 - Nausea/vomiting
 - Constipation
 - Diarrhea
 - Gastroparesis
 - Hematemesis
 - Melena
 - C. difficile colitis
 - Gastritis
 - Esophagitis
 - Gastric/duodenal ulcer
 - Decreased appetite
 - Gastroesophageal reflux disease
 - Ileus

- Partial intestinal obstruction
- Malnutrition/anorexia
- Systemic fever/pain/malaise/weakness
- Respiratory
 - Wheezing
 - Cough
 - Pleurisy
 - Pleural effusion
 - Pneumothorax
 - Bronchospasm
 - Diaphragmatic paralysis
 - Intra-pulmonary shunt
 - Caustic lesions
 - Bleeding secondary to biopsy
- Cardiovascular observations
 - Phlebitis
 - Arrhythmias
 - Hypertension
 - Cold extremities
 - Pericarditis
 - Tamponade
 - Myocardial ischemia
 - Heart failure
 - Pericardial effusion
 - Peripheral edema
 - Hyper/hypotension
 - Hyperlipidemia
 - Deep vein thrombosis
- Neurological
 - Hallucinations
 - Confusion
 - Headaches
 - Insomnia
 - Psychosis
 - Neuropathy
 - Anxiety
 - Depression
 - Tremor
 - Visual disturbances
- Head/Eyes/Ears/Nose/Throat:
 - Sinusitis
 - Sore throat
 - Hoarseness
 - Paralyzed vocal cord
 - Cough

- Epistaxis
- Thrush
- Herpes
- Renal/Genitourinary
 - Urinary tract infection
 - Urinary retention
 - Dysuria
 - Hematuria
 - Renal failure
 - Azotemia
 - Dehydration
 - Electrolyte imbalance
- Hematological
 - Anemia
 - Leukopenia
 - Thrombocytopenia
 - Pancytopenia
 - Leukocytosis
 - Coagulopathy
- Musculoskeletal
 - Myopathy
 - Tendonitis
 - Deconditioning
 - Weakness
 - Osteoporosis
 - Fracture
 - Pain
 - Osteonecrosis
- Endocrinological
 - Osteopenia
 - Diabetes
 - Decreased testosterone
 - Vitamin D deficiency
 - Hyper/hypothyroidism
 - Adrenal insufficiency
 - Cushingoid changes

Events Related to Study Endpoints

Any adverse events that are also defined within the primary and secondary endpoints do not require reporting as AEs since these are reported within the CRF. For example, PGD within the first 72 hrs or subject death does not require separate AE reporting from the Study Center since these events are captured via CRF. However, if a subject death was the outcome of a fatal SAE, then that SAE should be captured on the CRF. Additionally, if an AE defined as a primary or secondary endpoint meets the UADE criteria, expedited reporting is required.

